The current study focused on individuals with an established diagnosis of PTSD. The aim of the study is to investigate the effects of guided ICBT on measures of PTSD symptoms, depression, and other anxiety symptoms, as well as quality of life against a control group and the maintenance of the improvements. We expect that the effect size for program PAXPTSD to be in accord with other programs delivered to PTSD patients (Ivarsson et al., 2014; Knaevelsrud et al., 2015; Kuester, Niemeyer & Knaevelsrud, 2016; Spence et al., 2011; Sijbrandij, Kunovski & Cuijpers, 2016).

METHODS/DESIGN

The study is reported in line with the CONSORT 2019 statement (Consolidated Standards of Reporting Trials) and the SPIRIT 2013 Statement (Standard Protocol Items: Recommendations for Interventional Trials).

This study is a two-armed randomized controlled trial (RCT) with one active treatment condition (TC) and a waiting list control group (WL). Individuals from WL will receive the intervention 3 months after the study begins.

1. Guided internet-based cognitive behavioral program for Posttraumatic Stress Disorder (PAXPTSD): Participants will complete the PAXPTSD with guidance from a psychologist. The guidance includes a kickoff meeting discussion of approximately 30 minutes, via Skype, videoconference or telephone after the evaluation, to discuss the results of assessments and to discuss the next steps. After the completion of every module, the psychologists will schedule a session for Q & A with every participant to answer their questions, monitor their progress and offer them feedback. At the end of the program there will be another 30 minutes discussion for debriefing using Skype, videoconference or telephone. All participants will complete the standard program for general symptoms of PTSD and it is composed from 11 modules. Besides these modules, there are 5 facultative modules for specific aspects associated with PTSD (depression, guilt, shame or anger). Facultative modules are activated for every participant by his psychologist according to co-morbidity symptoms.

2. *Waiting list control group*: participants from this group will not receive any kind of intervention for 12 weeks. At the end of the waiting period the participants will receive the intervention program if they want this (after 3 months of study begins) and we will check if they receive any treatment for PTSD and associated problems in this period.

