Eligible participants are contacted by email to schedule a semi-structured clinical interview face to face or via telephone. The interviews are conducted by two trained clinical psychologists, independent from the study intervention, to verify and confirm the presence of PTSD and the conformity with all the inclusion and exclusion criteria. The eligible participants will receive an email from the administrator of the study with a link where there is a detailed informed consent to the participation in the study. The pre-treatment questionnaires will be completed on the platform by those who are eligible. Participants who offer consent and fulfill all the inclusion criteria are then randomly allocated to one of the two study groups, the treatment condition (TC) or the wait-list control (WL).

Participants in the TC will receive immediate access to the platform and online intervention while the participants in WL will receive login access after 3 months of study intake. After completing the evaluation phase all participants receive a short description and debriefing from psychologists in a kick off meeting of 30 minutes. Participants will receive access to each module after they complete the previous one (one module per week).

[figure not shown]

FIGURE 1 | Study flow

Interventions Development and Content

The PAXonline Standard Program for Post Traumatic Stress Disorder contains 11 modules. Besides these modules, there are 5 facultative modules for specific symptoms associated with PTSD (depression, other secondary emotions such as guilt, shame or anger). The program PAXPTSD contains modules which address important cognitive and behavioral psychotherapy elements which are detailed in **Table 3**. The treatment modules and the manual used to guide the intervention in our RCT were written based on *PAXOnline manual* and on the empirically validated cognitive behavioral models of anxiety disorders (Ciuca, 2019; Clark & Beck, 2011; Leahy, Holland & McGinn, 2011; Resick, Monson & Chard, 2014). The intervention content contains text, audios, short educational video clips, videos and interactive elements like quizzes. Each module can be completed in 15-40 minutes and the participants are provided with a recommended timetable (one or two modules per week, depending if there are necessarily additional modules) (Ciuca, 2019; Miclea, Miclea, Ciuca, Budau, 2010).

Table 3 PAXOnline Posttraumatic Stress Disorder Intervention

Standard program	Short description

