The Credibility/Expectancy Questionnaire (CEQ) (Deville & Borkovec, 2000) is used to measure expectancy for change and treatment credibility. Questionnaire contains 6 items, 4 about thinking and 2 about feelings, all 6 items are rated on a Likert scale and scores range from 1 to 9. The questionnaire has good internal consistency (expectancy $\alpha = .79-.90$; credibility $\alpha = .81-.86$) and test-retest reliability (expectancy = 0.82; credibility = 0.75) (Ciuca et al., 2011; Devilly & Borkovec, 2000). We administer CEQ in IG twice, after the first and fifth session.

Perceived social support

We use SS-5, which is an abbreviated version of the Medical Outcome Study Social Support Scale (MOS-SSS) (Sherbourne & Stewart, 1991). SS-5 is a 5 item short and reliable measure for assessing perceived social support, a predictor or possible moderator of treatment outcome. Participants are asked to rate each item on a 5-point Likert scale (1 to 5), the items are summed for a total score ranging from 5 to 25. Test-retest reliability for SS-5 is adequate (0.92) and also the internal consistency ($\alpha = .88$). In the scientific literature the equivalence between paper pencil administration and web-based administration was demonstrated of SS-5 (Ciuca et al., 2011).

Sociodemographic questionnaire

To evaluate sociodemographic characteristics of the participants we use a survey with 7 items which refer to: environment (urban or rural), ethnicity, marital status, education, occupation, income levels and computer skills (1 to 10) (Ciuca et al., 2011).

Adherence to treatment and homework compliance

We will assess adherence to treatment and homework compliance. We will analyze several aspects to identify potential mediating effects: number of modules completed, total time spent on the platform, time spent on each module, and usage of the support (Ciuca et al., 2011).

Patient satisfaction

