The effect size for iCBT intervention for PTSD is considered to be small to medium (Kuester, Niemeyer & Knaevelsrud, 2016; Lewis et al., 2019; Sibrandij, Kunovski & Cuijpers). Take this information in consideration we expected an effect size of .60. Based on this effect size, a power of .80 and a level alpha of 0.05 we would need 45 participants in each condition for testing the two tails hypothesis. This recommended sample size has been increased to accommodate an attrition rate of 20%. Thus, the study aims to achieve a total sample of 108.

Statistical analysis

All statistical analyses will be performed using the IBM SPSS Statistics version 20. The aim analysis will be conducted on intention-to-treat samples. We will use a linear mixed effects models approach with full information maximum likelihood estimation. This approach was recommended since it uses all available data and can handle missing data appropriately (Gueorguieva & Krystal, 2004; Meyer et al., 2015; Pond, 2011). The approach emphasizes the assumption that data are randomly missing and does not assume that missing data remain stable as in the last-observation-carried-forward (LOCF) approach (Blankers, Koeter & Schippers, 2010; Meyer et al., 2015). Significance testing of dichotomous data such as diagnostic status will be conducted with chi-square tests. Calculation of within and between- groups effect sizes (Cohen d) will be based on the pooled standard deviations. Regression analyses will be used to identify predictors of treatment outcome. Moderation and mediation analysis will be conducted with multiple regression models, using the PROCESS macro for SPSS (Hayes, 2017), a computational technique that can compute both simple and complex moderation and mediation models. Effect sizes for significant effects will be indicated by Cohen's d.

Consistent with recommendations from CONSORT (Schulz, Altman, Moher, 2011) and SPIRIT (Chan et al., 2013) we mention our intention to perform secondary analyses for minimal treatment users, defined as participants that complete at least 5 of recommended modules and use the intervention program for at least 80 minutes. This definition is based on the specific of our intervention program and the criteria used in other studies (Ciuca et al., 2011; Meyer et al., 2015; Ivarsson et al., 2014).

Discussion

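### Platform usage is listed as a possible mediator, but module use is zero in the whole waiting list up to T3, so a regression mediation model with arm as predictor can show mediation when treatment does nothing

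*Protocol*

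**What the plan says.** The adherence section of the Protocol lists four usage measures to be analysed "to identify potential mediating effects: number of modules completed, total time spent on the platform", time per module and use of support. The Statistical analysis section gives the method: "Moderation and mediation analysis will be conducted with multiple regression models, using the PROCESS macro for SPSS". The same section plans to "perform secondary analyses for minimal treatment users". It names no comparison group for them. To count as such a user, a TC participant must "complete at least 5 of recommended modules and use the intervention program for at least 80 minutes".

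On the control arm, the design section states that "participants from this group will not receive any kind of intervention for 12 weeks", and the Procedure section that "participants in WL will receive login access after 3 months of study intake". The post-assessment T3 is 11 weeks after randomisation. The main analysis is by intention to treat.

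**The concern.** A mediator has to be able to vary in both arms if a between-arm mediation model is to tell it apart from treatment. Module count cannot: throughout the controlled period it is zero for everyone on the waiting list. The only information on how usage relates to outcome then comes from TC participants, who chose how much to use. The Drop-out reasons section itself lists low motivation, worsening and improvement as reasons to stop, so a link between usage and prognosis is plausible.

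The minimal-user definition has a related weakness. It selects on two things observed after randomisation, and no WL participant can meet the module criterion.

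At stake is a published statement that the programme works through usage, or works better in those who use it, when the data may show only that participants with a better prognosis complete more modules.

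**Working it through.** The Protocol gives no figure for either analysis, so there is none to reproduce.

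**Inputs from the Protocol.** Total sample 108, so 108/2 = 54 per arm. Module use is zero in WL to T3. Table 3 lists 12 standard modules (the text says 11). The threshold is 5 modules.

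**Assumptions (not in the Protocol).** The correlation ρ between usage and outcome within TC is 0 to 0.4. TC usage is normal, clipped to 0–12, with mean 8 and SD 3 or mean 6 and SD 4. The outcome has SD 1, and treatment has no effect on anyone.

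**Mediation model.** Regress outcome Y on arm X and usage M, with M = 0 in WL.

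- Path a (arm to usage) = mean usage in TC.
- Path b (usage to outcome, given arm) = slope within TC, since WL has no spread in M. Its expected value is ρ/SD(M).
- Indirect effect = a × b ≈ ρ × mean(M)/SD(M).
- Direct effect = total − indirect, which is −(indirect) when the total is zero.

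At ρ = 0.3 this gives 0.3 × 8/3 = 0.80 SD, or 0.3 × 6/4 = 0.45 SD. Clipping raises both a little in simulation.

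The test statistic for b is roughly ρ√54, in which the usage distribution cancels:

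- ρ = 0.2: 1.47, so rejection is about P(Z > 0.49) = 31%.
- ρ = 0.3: 2.20, so about P(Z > −0.24) = 59%.
- ρ = 0.4: 2.94, so about P(Z > −0.98) = 84%.

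Simulation of null trials (4,000 per setting, Sobel test):

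| ρ | Indirect effect, mean 8 SD 3 | Indirect effect, mean 6 SD 4 | Indirect effect significant | Intention-to-treat test significant |
|---|---|---|---|---|
| 0 | 0.00 | 0.01 | 5% | 4–5% |
| 0.2 | 0.56 | 0.33 | 30–31% | 5% |
| 0.3 | 0.84 | 0.50 | 57–59% | 5% |
| 0.4 | 1.13 | 0.67 | 84–85% | 5% |

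The direct effect is equal and opposite in every row. With 45 per arm and a Monte Carlo interval instead of the Sobel test, the false-positive rates at ρ = 0.2, 0.3 and 0.4 are 27%, about 51% and 77%.

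**Minimal users against all of WL.** If a share p of TC qualifies and those are the heaviest users, the bias is ρ × φ(z)/p, where φ(z) is the normal density at the cut-off.

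- p = 0.60: 0.386/0.60 = 0.64.
- p = 0.84: 0.242/0.84 = 0.29.
- p = 0.88: 0.202/0.88 = 0.23.

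The shares follow from the two usage distributions. Mean 6 and SD 4 puts 60% at 5 modules or more. Mean 8 and SD 3 puts 84% there, or 88% if counts are rounded. Simulated results, in SD units and type I error:

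| ρ | 60% qualify | 84% qualify | 88% qualify |
|---|---|---|---|
| 0.2 | 0.13; 9–10% | 0.06; 6% | 0.045; 5% |
| 0.3 | 0.19; 14% | 0.08; 7% | 0.065; 6% |
| 0.4 | 0.26; 22% | 0.11; 9% | 0.09; 8% |

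The 80-minute criterion is not modelled. It could only lower the share that qualifies.

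**The case against.** The Protocol writes down no mediation model. It names the usage measures and the software, but not which variable is predictor, mediator and outcome. A model within TC alone would fit the wording, for example expectancy (measured only in the intervention group) to modules to outcome. The WL-at-zero mechanism would then not arise, although the usage–outcome leg would still be non-randomised. An analysis plan that is not shown may settle this. The objection stands to this extent: the fault is conditional on arm being the predictor, which is the usual question in a trial but is not stated.

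Several stronger readings are tempting and not supported.

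- A reader might infer that all four measures are zero in WL. That is certain only for module count and module time. Self-report assessments run inside the platform, and the Procedure section gives every participant a kick-off meeting, so platform time and support use may not be exactly zero.
- A reader might infer that minimal users will be compared with WL. No comparator is named.
- A reader might infer that a false result is bound to occur, or must favour the programme. At zero correlation both analyses hold 5%, and the sign could reverse if those who improve stop early.
- A reader might infer that the 5-module threshold misses the trauma-directed content. Table 3 places progressive desensitization in Module 5, and the threshold is a floor. Nothing in this point rests on module content.

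**Conclusion.** The point holds in conditional form. With arm as predictor, testing module use as a mediator cannot separate mechanism from self-selection. The false-positive rate is about 30% to 84% for an assumed correlation of 0.2 to 0.4, and hardly depends on the assumed usage distribution. The size of the false indirect effect does depend on it, and ranges from roughly 0.3 to 1.1 SD.

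The minimal-user problem is smaller and arises in this form only if the comparator is all of WL: about 0.04 to 0.26 SD, with type I error of about 5% to 22%, for 60% to 88% qualifying. The correlation and the qualifying share are both assumptions.

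A reader might take this as a threat to the trial's main conclusion. It is not: the minimal-user analysis is labelled secondary, the mediators are only called potential, and the intention-to-treat test keeps its level in the same simulated trials. The change is still worth making before the data are analysed, because the Protocol itself names these mediators and this method.

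**What to change.** In the adherence and Statistical analysis sections:

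1. State that usage will not be tested as a mediator of the randomised effect. Report the usage–outcome association within TC only, adjusted for baseline values and labelled non-causal.
2. Limit between-arm mediation to variables measured in both arms before the outcome, for example PTCI at T2 to symptoms at T3, adjusted for T1 values. State two limits. T2 (5 weeks in the Procedure section, 6 in Table 2) falls around Module 6, where cognitive restructuring is taught, so it may be early. And PTCI is not randomised, so mediator–outcome confounding remains.
3. Label the minimal-user result descriptive and not a randomised comparison. Alternatively, supplement it with a complier-average effect that uses randomisation as the instrument for reaching the threshold. State that this assumes no effect below the threshold. That is doubtful here, because participants who complete 1 to 4 modules still receive content and question sessions, and any benefit to them would inflate the estimate.

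The cost is wording and a little programming. PTCI at T2 is already scheduled, and WL is assessed like TC. The complier estimate is roughly the intention-to-treat effect divided by the qualifying share, so its confidence interval widens by about 1/0.60 = 1.67 times if 60% qualify, or 1/0.84 = 1.19 times if 84% do.

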Clinician interviewing and self-report assessments will take place at screening (T0), pre-treatment assessment (T1), post-assessment 11 weeks after randomization (T3) and 3 months follow-up (T4). There will be also weekly mood assessment. All self-report measures are administered through internet (secure links are used and all the data are

encrypted) and the diagnostic interviews are conducted face to face or via telephone. The questionnaires, which were not yet validated for Romanian population, were previously translated in Romanian and underwent a rigorous back-translation process to ensure a good adaptation. The version we acquired was approved by the author(s) of questionnaires. See **Table 2** for an overview of all assessments. Adherence to assessment completion will be monitored throughout the study. In case of noncompliance participants will be contacted after 7 days (14, 21) to remind them of assessment completion. After 28 days a short message will be sent via text message. The entire communication between psychologist and participants will be inside the platform. In maximum 48 hours after completing the module the psychologist and the participants will schedule the Q and A session for any questions, they will also give feedback and monitor the progress.

Persons who are interested in the program can freely access the study website. The website offers information about PTSD and treatment options and a description of the present clinical trial and information about enrollment.

Participants must offer an online informed consent, and then provide demographic information (age, gender, location and contact information). Then, they have to complete key questionnaires: (1) a screening for the exclusion criteria; (2) one scale to evaluate Posttraumatic Stress Disorder and its severity (PDS-5); and (3) a screening questionnaire for psychiatric comorbidities using Psychiatric Diagnostic Screening Questionnaire (PDSQ).

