Psychiatric diagnostic and screening questionnaire	PDSQ	Axis 1 disorders	Pre-treatment, post-treatment and follow-up (3 months)
Perceived stress scale - 10	PSS-10	Perceived stress levels	Pre-treatment, middle intervention assessment (after 6 weeks), post-treatment and follow-up (3 months)

Additional measures

Credibility/ expectancy questionnaire	CEQ	Expectancy for change and treatment credibility	Administered to 2 and 5 weeks during intervention
A 5-item shortened version of the Medical Outcomes Study Social Support Scale (MOS-SSS)	SS-5	Social support	Pre-treatment, middle intervention assessment (after 6 weeks), post-treatment and follow-up (3 months)
The Patient Feedback Questionnaire	PFQ	Evaluate the patients' satisfaction with the platform, quality and utility of program.	Post-treatment assessment
Positive and Negative Effects of Psychotherapy Scale	PANEPS	Evaluate negative side effects of intervention.	Post-treatment

Diagnostic interview

Comorbidities are assessed using the Romanian adapted version of Psychiatric Diagnostic Screening Questionnaire (PDSQ) (Ciuca, Berger, Crisan, & Miclea, 2016; Ciuca, Berger, Crisan, & Miclea, 2018), which comprises a self-report screening scale, followed by a semi-structured interview delivered by a clinician. The PDSQ scale has good psychometric properties. In the Romanian validation study the mean of the alpha coefficients was .85 and test-retest reliability was above .80 for nine subscales, with a mean test-retest of .85 (Ciuca et al., 2016). Following the screening procedures, all eligible participants are interviewed by one of the psychotherapists. Any mental disorder that reached PDSQ screening cutoff point is assessed during the interview. In order to increase interraters' agreement on assessment protocol, the assessors have to participate in a two days training before study starts. The diagnostic interview is conducted before and after the treatment by clinicians blind to the treatment group. At post-treatment diagnostic interview we are going to count missing data as equivalent to still meeting diagnostic criteria for Posttraumatic Stress Disorder. The procedure is recommended according to intention-to-treat paradigm and was used in several other studies (Hedman et al., 2013; Weisel et al., 2018).

Primary outcomes

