We will use The Patient Feedback Questionnaire (PFQ). The questionnaire was used in a previous study which evaluates the efficacy of an iCBT program for panic attacks and it was developed by a team of researchers (Ciuca et al., 2011). The questionnaire contains 14 items which evaluate the patients' satisfaction with the platform and several other aspects (quality and utility of different components of the platform). Other items refer to giving improvement suggestions, what they like most, if they would use it again or recommend it to a friend with symptoms related to traumatic experiences. The questionnaire will be administered at post-treatment evaluation.

Drop-out reasons

In order to evaluate the reasons for drop-out we will use a questionnaire developed by Ciuca et al. The questionnaire contains 18 items and each item is considered to be a possible reason (e.g. lack of motivation, lack of time, different expectations, exacerbation of symptoms, interface is too complicated, the treatment pace is too slow or too fast, finding another treatment, getting better, important life events etc.) (Ciuca et al., 2011).

Side effects

We will evaluate negative side effects after completion of the intervention to identify any negative effects of PAXPTSD program. For this at the end of the program, participants will complete the Positive and Negative Effects of Psychotherapy Scale (PANEPS) (Moritz et al., 2018). PANEPS was evaluated in a population of individuals with depression who had completed at least one course of face-to-face psychotherapy. Factor analysis yielded four dimensions: positive effects, side effects, malpractice, and unethical conduct. Internal consistency of PANEPS range between 0.72 - 0.92 (Herzong, Lauff, Rief & Brakemeier, 2019).

Randomization

Participants who return the informed consent and meet all the required criteria are randomly allocated to one of the two conditions . The randomization process is done by a software that was developed to implement a minimization algorithm (Pocock & Simon, 1975) that assures a balanced randomization between groups with respect to certain predefined prognostic (stratification) factors. In this study, two stratification factors have been considered:

SEVERITY(4 levels according to PDS-5 screening scores; level 1: 11 to 23 points; level 2: 24 to 42 points; level 3:

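### The negative-effects scale (PANEPS) is timed to programme completion, and no text gives it to treatment-arm participants who stop early

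*Protocol*

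**What the plan says.** Four parts of the protocol bear on when PANEPS is given and to whom.

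- **Side effects.** "We will evaluate negative side effects after completion of the intervention". The next sentence repeats the timing: "For this at the end of the program, participants will complete the Positive and Negative Effects of Psychotherapy Scale".
- **Table 2, additional measures.** PANEPS has the aim "Evaluate negative side effects of intervention" and one administration, listed as post-treatment. No restriction to completers is given.
- **Procedure.** The post-treatment visit is a calendar time: "post-assessment 11 weeks after randomization (T3". Missed assessments trigger reminders at 7, 14 and 21 days and a text message after 28 days.
- **Drop-out reasons.** An 18-item questionnaire asks why people left. One listed reason is "exacerbation of symptoms"; others include improvement and shortage of time.

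Harm can also surface elsewhere. Under Guidance and Adherence Monitoring, psychologists watch for deterioration, and crises and adverse events go to the research team. The PCL-5, PHQ-9 and GAD-7 are collected weekly (Table 2).

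**The concern.** PANEPS is the only instrument designated for negative effects, and the Side effects section ties it to finishing in two consecutive sentences. Visit-based wording was available: the Patient satisfaction section attaches its questionnaire to the post-treatment evaluation.

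Modules open one after another. Table 3 places desensitisation, confrontation with the traumatic memory and the two exposure modules at numbers 5 and 7 to 9. A participant who stops there has not reached the end of the programme. The protocol foresees partial use, since the Statistical analysis section defines a minimal user as someone with at least 5 modules and 80 minutes.

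If such people are not asked, the reported frequency of negative effects describes those who got through the programme. A later analysis plan could not repair this, because the answers would never have been requested.

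**Working it through.** The protocol states no figure that depends on this point, so there is none to reproduce. The check compares the texts and then shows how the size depends on unknown rates.

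**1. Who is asked under each text**

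| Place | Trigger for PANEPS | Does it reach someone who stopped? |
|---|---|---|
| Side effects | end of the programme | No, if read literally |
| Table 2 | post-treatment | Not stated |
| Table 2 read with Procedure | T3, 11 weeks after randomisation | Yes, if the person still answers assessments |

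**2. Are programme end and T3 the same event?** Not necessarily. The Procedure section gives one module per week, while the section on intervention content allows one or two. The text counts 11 standard modules, but Table 3 lists 12. At one per week, a twelfth module falls in week 12, after an 11-week T3. So the two triggers can separate even for people who finish. The module counts also need reconciling.

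**3. Illustrative size**

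Inputs from the protocol: total sample 108 and attrition 20% (Sample size). Assumptions: equal arms, everyone lost to attrition misses PANEPS, and the harm rates below.

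- Treatment arm: 108 / 2 = 54.
- Missed: 54 × 0.20 = 10.8, about 11. Reached: 54 − 11 = 43.
- Whole-arm rate = (43 × rate in completers + 11 × rate in stoppers) / 54. PANEPS in completers alone shows the completers' rate.

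| Completers (reported) | Stoppers | Whole arm | Reported / whole arm |
|---|---|---|---|
| 5% | 5% | 5.0% | 100% |
| 5% | 25% | (2.15 + 2.75) / 54 = 9.1% | 55% |
| 5% | 50% | (2.15 + 5.50) / 54 = 14.2% | 35% |
| 10% | 10% | 10.0% | 100% |
| 10% | 25% | (4.30 + 2.75) / 54 = 13.1% | 77% |
| 10% | 50% | (4.30 + 5.50) / 54 = 18.1% | 55% |

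With 10% to 30% missed (5 to 16 of 54) and the same rates, the last column runs from 100% down to 27%. The lowest value comes from 30% missed with rates of 5% and 50%: (38 × 0.05 + 16 × 0.50) / 54 = 18.3%, and 5 / 18.3 = 27%.

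The sign can also reverse. With 10% in completers and none in stoppers, the whole-arm rate is 4.30 / 54 = 8.0%, and the reported 10% is too high.

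**The case against.** The strongest reply is that the Side effects wording names a time and not a population. Table 2 has no completer restriction, T3 is fixed by the calendar, and reminders follow missed assessments. Where the protocol wants a subset defined by usage, it defines one. This reading is possible and it stands as such: the documents do not establish that stoppers will be excluded. It does not settle the matter, because the section devoted to side effects uses a different trigger and no text says that stoppers receive the scale.

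A reader might infer three stronger things that the documents do not support.

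- *That harm is measured only after completion.* Weekly symptom scores, adverse-event reporting and the drop-out questionnaire do not depend on finishing. They are only a partial substitute. A reason for leaving is not a frequency of negative effects, symptom scores do not cover the side-effect, malpractice and unethical-conduct dimensions of PANEPS, and adverse events are reported without any stated systematic enquiry.
- *That the bias always favours the intervention.* People also leave because they improved or lack time. With no excess harm in stoppers the bias is zero, and with less harm it reverses.
- *That PANEPS is defective for lack of a control comparison.* It rates effects of psychotherapy, and a waiting list has received none to rate.

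The objection to the arithmetic also stands. The 20% is a sample-size allowance, not a rate of stopping modules. If those people are lost to every assessment, a T3 mailing would miss most of them. If they still respond, the Table 2 reading may already reach them.

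**Conclusion.** The point holds as a gap and an inconsistency in data collection. PANEPS is timed to programme completion in one section and to post-treatment in another, and nothing assigns it to participants who discontinue. Followed literally, early stoppers may be missing from the only dedicated harm measure. Negative effects would then be understated if worsening makes stopping more likely.

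The size cannot be fixed from the protocol. The illustration rests on equal arms, on assumed harm rates, and on reading the 20% attrition as the share missing PANEPS. Under those assumptions, a reported 10% would correspond to 10.0% to 18.1% in the whole arm.

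The primary analysis is not affected. The change is still worth making before enrolment, because it concerns what is asked of participants.

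**What to change.** Reconcile the Side effects section, Table 2 and the Procedure section. State that PANEPS is sent at T3, 11 weeks after randomisation, to every treatment-arm participant who started any module, whether or not the programme was finished. State that it is also sent when a participant stops, for example together with the drop-out questionnaire. Report the PANEPS response rate by completion status.

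As a supplement, report the proportion who worsened on the PCL-5 and PHQ-9, treatment against waiting list. These scores are already scheduled, and the Methods section has waiting-list participants complete assessments similar to those of the treatment arm. The definition of worsening can be left to the analysis plan.

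The cost is a short text edit and one more automatic link on the platform, which can use the existing reminders. There are two downsides. Response among non-completers will probably be lower. The protocol also describes PANEPS as evaluated in people with at least one finished course of face-to-face therapy, so use after a few modules goes beyond that evidence and the report should say so.
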